#### **1.6.1 Power analysis**

In a previous iteration of this study with soft spherical contact lenses, typical inter-subject standard deviation values on a 0-100 scale for comfort, vision [REDACTED] (at lens dispensing) were 13.4, 14.1 and 13.7 units, respectively. Assuming an equivalence margin of seven units and an alpha of 0.5, data from 44 subjects are required to provide power of 0.90 or greater for equivalence testing for these three parameters. To allow for any inadequate lens fits, up to 50 subjects will be recruited for this work.

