#### 2.1.1 Subject withdrawal and replacement

This study is a single clinical visit study. Once the study consent form is signed, the subject is considered to be enrolled on the study. Subjects who have signed the consent form, but who have not had the first lens applied to the eye will usually be replaced. All subject data will be included in the final analyses unless there are strong grounds for exclusion; such grounds will be detailed in the final report.

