### **3.4 Missing, unused and spurious data**

The absence of any data will be carefully and critically considered. If appropriate, partial datasets will be included in the final analysis. Any data missing from a subject visit will be outlined in the report by indicating the number of subjects included for each analysis. Data that are unused or considered to be spurious will be detailed and discussed in the report.

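### Does the allowance for inadequate lens fits, with exclusion grounds left open, bias the lens comparison towards equivalence?

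*Combined protocol and SAP*

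**What the plan says.** Section 1.6.1 (Power analysis) states that "data from 44 subjects are required" and gives one reason for going above that number: "To allow for any inadequate lens fits, up to 50 subjects will be recruited for this work". The Study summary describes the same gap in terms of consent and completion: up to 50 consented, at least 44 completing.

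On who is analysed, section 2.1.1 says: "All subject data will be included in the final analyses unless there are strong grounds for exclusion". It adds that any such grounds will be set out in the final report. Section 3.4 allows partial datasets into the analysis where suitable, promises the number of subjects behind each analysis, and says: "Data that are unused or considered to be spurious will be detailed and discussed in the report".

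In section 3.2.2, fit on the first lens is checked about one minute and again fifteen minutes after application, each time before the subject gives scores. The text straight after the fit criterion is redacted, as is much of section 1.6. The visible part of section 1.6 names linear models or another parametric approach, and does not limit the analysis to subjects with scores on both lenses.

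**The concern.** If six places are set aside for inadequate fits, the natural reading is that poorly fitted subjects do not count towards the 44. Fit is a result of the lens, not a baseline characteristic, so leaving such subjects out would keep only those for whom both lenses worked. When the aim is to show similarity, removing subjects who do badly on one lens can pull the means together, and the error then favours the claim.

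Three features add to the worry. The grounds for exclusion, and the meaning of spurious data, are not defined in the visible text. The visible text masks only the subject, and every subject wears the lenses in the same order, so lens identity is plain from the period. And a subject who stopped after the first lens would have no scores on the second, so an analysis of complete pairs would lose that subject altogether. At stake is the validity of an equivalence claim against a 7-unit margin.

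**Working it through.** **1. Reproducing the 44.** Inputs from section 1.6.1: "Assuming an equivalence margin of seven units"; standard deviations that "were 13.4, 14.1 and 13.7 units, respectively"; "power of 0.90 or greater for equivalence testing for these three parameters"; and "an alpha of 0.5". For two one-sided tests on paired differences with a true difference of 0:

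n = (SD × (z(1−α) + z(1−β/2)) / margin)²

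With α = 0.05 and SD = 14.1: (14.1 × (1.645 + 1.645) / 7)² = 43.9, so 44. SDs of 13.7 and 13.4 give 42 and 40. With α as printed, z(0.5) = 0 and n = (14.1 × 1.645 / 7)² = 11. The 44 therefore reproduces with α read as 0.05 and the quoted SD taken as that of the paired difference. Both readings are used below; neither is the subject of this point.

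**2. The allowance.** 50 − 44 = 6, and 6/50 = 12%. At SD 14.1 the t-based power is 0.931 with 50 subjects and 0.890 with 44.

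**3. Largest shift if every poor fit were dropped.** With all failures on one lens, shift = 0.12 × score penalty. The documents give no penalty, so a range is assumed:

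| Assumed penalty (units) | Shift (units) | Share of the 7-unit margin |
|---|---|---|
| 10 | 1.2 | 17% |
| 20 | 2.4 | 34% |
| 30 | 3.6 | 51% |
| 40 | 4.8 | 69% |

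**4. A worked adverse case.** Let 44 subjects have a mean difference of 5 and six a mean difference of 22. The overall mean is (44 × 5 + 6 × 22)/50 = 7.04, just outside the margin. Analysing only the 44 declares equivalence with probability 0.251, 0.245 or 0.236 for SD 13.4, 13.7 or 14.1, against 0.05 at a true mean of 7. The arithmetic is right, but the values 5 and 22 are chosen to land on the margin.

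**5. Whether the direction is fixed.** Simulated trials of 50 subjects (40,000 runs per row, SD of differences 14.1, one-sided α 0.05), with differences taken as first lens minus second:

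| Pattern of poor fits | Mean difference, all → after exclusion | Equivalence declared, all → after exclusion |
|---|---|---|
| 12%, worse lens only, 20-unit penalty | −7.0 → −4.6 | 5% → 29% |
| 12%, worse lens only, 40-unit penalty | −7.0 → −2.2 | 6% → 71% |
| 6% on each lens, 20-unit penalty | −7.0 → −7.0 | 5% → 5% |
| 12%, better lens only, 20-unit penalty | −4.6 → −7.0 | 28% → 5% |
| 6% on each lens, no effect on score | −7.0 → −7.0 | 5% → 5% |

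Exclusion favours equivalence only when failures concentrate on the worse-scoring lens. Otherwise it does nothing or works the other way. Table 2 in section 2.5.1 gives both lenses the same material, water content and base curve, with diameters of 14.0 and 14.1 mm. Nothing in the documents points to a large difference in fit failure.

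**6. Whether the plan calls for exclusion.** Set side by side, section 1.6.1 anticipates some inadequate fits, section 2.1.1 keeps all data by default, and section 3.4 admits partial datasets. These are compatible: someone who does not complete both lenses falls short of the completion target, yet the scores already recorded can still be analysed. No visible text says that a poor first fit ends the visit, and the examples of discontinuation reasons in section 2.2 do not include fit.

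**The case for a change.** The best case for a change is that reporting exclusions afterwards is not the same as specifying them beforehand. Fit is the only stated reason for the six extra places, so some fit-related loss is expected, and no visible rule says how an inadequately fitted subject is analysed. With lens order fixed and only the subject masked, a choice could be made with scores and lens both known. Even the reversed pattern shows a result that depends on an undefined choice, and a sentence of wording would cost little.

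Part of this stands. Fit is a post-application outcome, the grounds are undefined in the visible text, and stating that poor fit alone is no reason for exclusion would do no harm. The rest is weaker. Keeping every recorded score is already the default. A model that uses subjects with one lens is open to the analyst under section 1.6. The fit check precedes the scores in the visit steps, so a fit-based decision need not follow sight of them; the plan says that grounds are reported in the final report, not that they are decided there. Reporting fit failures by lens is good practice but alters no estimate. Requiring equivalence in both the full set and the adequately fitted pairs would make success hang on a second test, whose power at 44 pairs and SD 14.1 is 0.890 even with no true difference.

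**Conclusion.** No change is needed. This is a gap that an analyst fills sensibly by doing what section 2.1.1 already says, and followed that way the plan is free of the selection effect. The adverse figures (a 2.4-unit shift, and false equivalence rising from 5% to 29%) need four things together: all six places used, all failures on one lens, that lens being the worse-scoring one, and every such subject excluded against the default. They also rest on an assumed 20-unit penalty. Bias towards equivalence is therefore possible but not shown.

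The conclusion assumes that the all-data default is applied and that exclusions are disclosed as promised. The redacted text may already hold a fit rule. If the final report did show several fit-related exclusions mainly on one lens, a reader could gauge the effect as the share excluded times the score penalty.

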#### **1.7 Risk analysis**

This study is considered to be a non-significant risk study based on United States Food and Drug administration (FDA) and International Standards Organization (ISO) guidelines due to the daily wear nature of the study. With the potential benefit of this study, the work is considered to be ethically justifiable. Ethical approval will be sought from the University of Manchester Research Ethics Committee (hereafter referred to as Manchester UREC). The work where practical will be conducted in accordance with the ICH Good Clinical Practice Guidelines and the international standard BS EN ISO 14155: 'Clinical investigation of medical devices for human subjects'.

##### **1.7.1 Clinical trial registration**

This study will be registered on [www.clinicaltrials.gov](http://www.clinicaltrials.gov).

## Section 2. Resources

### 2.1 Subject selection

In this work, up to 50 subjects will be enrolled.

#### 2.1.1 Subject withdrawal and replacement

This study is a single clinical visit study. Once the study consent form is signed, the subject is considered to be enrolled on the study. Subjects who have signed the consent form, but who have not had the first lens applied to the eye will usually be replaced. All subject data will be included in the final analyses unless there are strong grounds for exclusion; such grounds will be detailed in the final report.

#### 2.1.2 Subject recruitment

Subjects will be recruited by one or more of following means:

1. Posting study details on The University of Manchester's 'Research Volunteers' website.
2. Correspondence to existing wearers on the Eurolens Research database of subjects.
3. Advertising through a variety of media via a format separately approved by Manchester UREC.

#### 2.1.3 Inclusion criteria

Subjects will only be eligible for the study if:

1. They are of legal age (18) and capacity to volunteer.
2. They understand their rights as a research subject and are willing and able to sign a Statement of Informed Consent.
3. They are willing and able to follow the protocol.
4. They currently wear soft contact lenses, or have done so within the past two years.
5. They are expected to be able to be fitted with the study lenses within the power range available.

#### 2.1.4 Exclusion criteria

Subjects will not be eligible if:

1. They have an ocular disorder which would normally contra-indicate contact lens wear.
2. They have a systemic disorder which would normally contra-indicate contact lens wear.
3. They are using any topical medication such as eye drops or ointment.
4. They are aphakic.

5. They have had corneal refractive surgery.
6. They have any corneal distortion resulting from previous hard or rigid lens wear or have keratoconus.
7. They are pregnant or lactating.
8. They have an eye or health condition including an immunosuppressive or infectious disease which would, in the opinion of the investigator, contraindicate contact lens wear or pose a risk to study personnel; or a history of anaphylaxis or severe allergic reaction.
9. They have taken part in any contact lens or care system clinical research within two weeks prior to starting this study.

## **2.2 Subject discontinuation**

In general, subjects should be discontinued at any time, if it is in their best interests, as judged by the investigator. Reasons for this may include clinical signs of grade 3 or more, lack of motivation, discomfort, repeated refusal to follow instructions or the use of non-study products such as solutions or lenses. Subjects will be discontinued if a serious adverse event occurs or if they miss two or more planned consecutive visits. Subjects who fail to satisfy all the inclusion and exclusion criteria will be discontinued and replaced. Subjects may choose to leave the study at their own request. All discontinuations will be carefully recorded.

## **2.3 Safety parameters, adverse events and concurrent illnesses**

The key safety parameters are the serious and significant ocular adverse events listed in Appendix A (adverse events are classified as 'serious', 'significant' or 'non-significant'). Clinical assessment is made at the study visit(s) for these parameters. The presence of an ocular adverse event will be reported on the case report forms and those described as 'serious' or 'significant' will be detailed in the final report. Similarly, any concurrent illness that is likely to impact on the relevance and quality of the captured data will be noted on the case report form.

### **2.3.1 Investigator obligations**

At all times the investigator will act in the best interest of the subject. Referral or treatment of an adverse event or other clinical finding should be initiated in the best clinical judgement of the investigator, irrespective of the participation in the clinical study.

### **2.3.2 Reporting obligations**

Adverse events will be reported to the sponsor in accordance with their reporting requirements. Manchester UREC and any regulatory authorities will be informed as required.

## 2.4 Protocol deviations

Any deviations from this protocol will be recorded and reported to the Sponsor Contact Person as appropriate. Manchester UREC will be informed as necessary.

## 2.5 Study resources

Study products will be stored according to the manufacturer's product instructions.

### 2.5.1 Lenses

Details of the lenses are provided in Table 2. Both lenses are CE marked and will be used within the terms of their product licence. Each lens pair will be worn for approximately 15 minutes in the clinic only. Lens foils will be overlabelled so that the subject is masked to the lens brand.

	Lens 1	Lens 2
Name	Live Daily Disposable	Clariti 1day
Manufacturer	CooperVision Inc	CooperVision Inc
Material	Somofilcon A	Somofilcon A
EWC (%)	56	56
Base Curve (mm)	8.6	8.6
Diameter (mm)	14.0	14.1
Spherical powers (DS)	-1.00 to -6.00 (0.25 steps)	-1.00 to -6.00 (0.25 steps)

Table 2: study lenses.

#### 2.5.1.1 Use of lenses

Subjects will wear the contact lenses in the clinic only. (i.e. lenses will be removed at the end of the study visit and discarded).

#### 2.5.2 Care regimen

No care regimen will be used as the lenses are to be worn in the clinic only.

#### 2.5.3 Inventory control

The sponsor will supply both lens types. All worn lenses will be discarded.

## 2.6 Data collection and analysis

Data collected in this work will be recorded on a custom-developed database and an established data trail. Data handling will include export of the study information from the clinical database into spreadsheet format for manipulation, followed by export into a statistical package for analysis. Most clinical data will be entered directly onto the electronic case report form and are considered to be source data.

## 2.7 Study monitoring

In order to provide quality control and quality assurance as part of this work, the study monitor will:

1. Liaise closely with the Principal Investigator.

2. Monitor and ensure the safety of the subjects.
3. Ensure that the investigation is being conducted according to the protocol.
4. Monitor and review (or oversee review of) the study records to ensure accuracy.
5. Document their observations and make them available to relevant authorised parties (e.g. Manchester UREC).
6. Implement the Eurolens Research clinical monitoring standard operating procedure.

## Section 3. Subject management

### 3.1 Visit scheduling

Each subject will attend for a single study visit. Lenses will be worn for a defined period of time, with assessments occurring at various intervals, in accordance with the visit schedule detailed in this protocol. The subject will wear both of the study 'lens pairs' during the single study visit.

### 3.2 Visit conduct

Visit procedures are carried out in accordance with the relevant, current Eurolens Research Standard Operating Procedures.

#### 3.2.1 Pre-enrolment

The subject will receive a study-specific information form outlining the study at least 24 hours before the initial visit.

#### 3.2.2 Study visit

*Subjects should attend wearing their spectacles.*

They will then be required to sign an informed consent form prior to enrolment. A copy of the signed form will be issued to the subject. When the subject has signed the consent form, they are considered to be enrolled on the study.

Subjects will be instructed on the following:

1. Lens handling, application and removal, where necessary.
2. Specific study instructions, such as the importance of not using any other contact lens products.
3. General contact lens information such as the management of red eyes.

The following procedures will be performed (any ocular measurement procedures outlined below will be carried out on each eye).

1. Details of the ocular, medical and contact lens-wearing histories of the subject will be noted [REDACTED]
2. [REDACTED].
3. [REDACTED]
- [REDACTED]
- [REDACTED]
- [REDACTED]

4. [REDACTED]

[REDACTED]

5. The investigator will confirm that the subject satisfies all the inclusion and exclusion criteria. Subjects who fail to meet all the criteria at this time will usually be discontinued and replaced unless the reason is considered to be transient in which case a further visit can be scheduled.
6. The first lens pair, Live Daily Disposable, will be fitted selecting the closest available lenses for the subject based on refraction from the lens bank.
7. The subject will apply the lenses.

As soon as possible (*~1 minute after lens application*), lens fit will be assessed using the following evaluations: horizontal and vertical centration, corneal coverage and movement. Normally, for an acceptable fit, centration and movement will fall within currently accepted clinical criteria [REDACTED]

8. Distance high contrast monocular logMAR visual acuity will be recorded.
9. The subject will be asked to score the following subjective scores with reference to appropriate vertical visual analogue scales (0-100) [REDACTED]
  - Comfort
  - Vision
  - [REDACTED]
  - Overall score

10. [REDACTED]

11. Fifteen minutes after lens application, lens fit will be assessed (as above).

12. [REDACTED]

13. [REDACTED]

[REDACTED]

15. The subject will be asked to score the following subjective scores with reference to appropriate vertical visual analogue scales (0-100) [REDACTED]

- Comfort
- Vision
- Overall score

16. [REDACTED]

17. The contact lenses will be removed and discarded.

18. [REDACTED]

[REDACTED]

19. The second lens pair, Clariti 1day, will be fitted selecting the closest available lenses for the subject based on refraction from the lens bank.

20. The same procedures will be carried out for the second lens pair (Clariti 1day) as the first lens pair, points 8 to 18 (above).

21. [REDACTED]

[REDACTED].

22. [REDACTED]

23. At the end of the visit (or if the subject is discontinued earlier in the visit) the subject's payment will be processed and the subject discharged, although they may have been asked by the investigator to attend a post-study follow-up visit. They should continue to use their lenses and solutions as advised, and seek aftercare for their contact lenses.

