## Study summary

This subject-masked, non-randomised, crossover controlled non-dispensing study will compare the performance of Live Daily Disposable and Clariti 1day lenses, in a single study visit. Up to 50 subjects will be consented with the aim of completing at least 44 subjects. All subjects will first be fitted with the Live Daily Disposable lens and secondly with the Clariti 1day lens.

A summary of the study visit and procedures is provided in Table 1.

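### Does step 20 of the study visit give the second lens pair fewer procedures than the first, because its repeat starts at point 8?

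*Combined protocol and SAP*

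**What the plan says.** The relevant text is in section 3.2.2, Study visit, of the combined protocol and SAP.

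- **First pair (Live Daily Disposable).** Point 6 selects the lenses. Point 7 reads "The subject will apply the lenses". An unnumbered paragraph follows, timed at about one minute after application, in which "lens fit will be assessed using the following evaluations: horizontal and vertical centration, corneal coverage and movement". Point 8 is visual acuity: "Distance high contrast monocular logMAR visual acuity will be recorded". Subjective scores are taken at points 9 and 15. Between them, point 11 reads "Fifteen minutes after lens application, lens fit will be assessed (as above"). Point 17 removes the lenses.
- **Second pair (Clariti 1day).** Point 19 reads "The second lens pair, Clariti 1day, will be fitted selecting the closest available lenses for the subject based on refraction from the lens bank". Point 20 then reads "The same procedures will be carried out for the second lens pair (Clariti 1day) as the first lens pair, points 8 to 18 (above").

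The order is the same for everyone. The Study summary states: "All subjects will first be fitted with the Live Daily Disposable lens and secondly with the Clariti 1day lens".

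Section 1.4 names the overall score as primary, and comfort and vision as secondary. Further text in that section is redacted.

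**The concern.** Point 20 makes two statements that do not quite agree. It promises that the second pair is handled like the first, and then gives a range that starts one point too late for that to be literally true. Point 19 repeats only point 6. No numbered step therefore tells the subject to put the second pair in, and the fit check at about one minute falls outside the range.

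In a randomised crossover, a small procedural difference between periods would be spread over both lenses. Here it would not be. With Live always first and Clariti always second, anything done differently in the second period is done differently for Clariti, and no analysis can separate the two. If the early fit check were made for Live only, the early fit data would have no Clariti counterpart, and the first scores at point 9 would follow a fit examination for one lens but not for the other.

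**Working it through.** No arithmetic in the plan bears on this point. The check is to set the visible steps for the two pairs side by side.

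| Visible step | Live (first pair) | Clariti, literal reading of point 20 |
|---|---|---|
| Lens selection | Point 6 | Point 19 |
| Subject applies lenses | Point 7 | Not restated |
| Fit at about 1 minute | Unnumbered, between 7 and 8 | Not in range |
| Visual acuity | Point 8 | In range |
| Scores, first visible set | Point 9 | In range |
| Fit at 15 minutes | Point 11 | In range |
| Scores, second visible set | Point 15 | In range |
| Removal | Point 17 | In range |

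Points 10, 12, 13, 16 and 18 are redacted, and the number 14 does not appear in the extracted text. The table is therefore limited to what can be read and is not a full count of procedures.

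**Application of the second pair.** Three other places settle this. Section 3.1 says that each subject wears both pairs in the visit. Section 2.5.1 gives each pair about 15 minutes of wear. Point 11, which is inside the cited range, is timed from lens application. Acuity, scores, the 15-minute fit and removal cannot be done for a lens that was never put in. Nobody running the visit could conclude that the second pair is not applied.

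**The one-minute fit check.** This is the only visible item in real doubt.

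- Literal reading: visible fit checks are 2 for Live (about 1 minute and 15 minutes) and 1 for Clariti (15 minutes).
- Reading by the opening words of point 20: 2 and 2.

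The second reading is the more natural. The main clause of point 20 states equal treatment, and the range only points to where the steps are listed. To apply the lenses at all, staff must go back to point 7, and the fit paragraph sits directly beneath it. Point 11 also sends the reader back to that paragraph for what a fit assessment consists of.

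**Reach into the outcomes.** The visible scoring steps, points 9 and 15, are in the range for both lenses, so no primary or secondary score is lost for Clariti on either reading. A fit examination shortly before point 9 for one lens only is the one route by which the literal reading could touch a score. The documents give no figure for such an influence, and none is assumed here. Before the second visible set of scores, at point 15, both lenses have had the 15-minute fit check.

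**Reach into sample size.** Section 1.6.1 recruits up to 50 subjects so that 44 provide data, an allowance of 50 − 44 = 6 for inadequate fits. On the literal reading, Clariti fit is still assessed at 15 minutes, so a second pair that fits poorly would still come under assessment within the visit.

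**The case for a change.** The strongest case for a correction is that the early fit check, unlike lens application, is not implied by anything in points 8 to 18, since all of the visible steps there can be completed without it. Two careful readers could act differently. Section 2.7 asks the monitor to see that conduct follows the protocol, and section 2.4 asks for deviations to be recorded, so it is fair to ask whether leaving out the one-minute Clariti check would count as a deviation. Redaction does not remove the mismatch: points 7, 8, 19 and 20 are all legible, and the redacted text next to point 18 comes before the second pair is fitted. Because the order is fixed, the two lenses ought to be handled alike, and correcting a range is nearly free.

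Much of this stands. The range is wrong as printed, and the visible text does not settle the early Clariti fit check beyond its statement that procedures are the same. What does not stand is the step from there to a consequence for the trial. The confounding of lens with order comes from the non-randomised design set out in section 1.5, and a corrected range would leave it exactly as it is. Lens fit is not among the visible outcome measures. Table 1 is not shown, and section 3.2 places visit conduct under standard operating procedures that are not in the document. Either may already list the check for both pairs.

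**Conclusion.** This is a clerical slip in a cross-reference, and no change to the plan follows. The range in point 20 starts after point 7 and the fit paragraph beneath it, while the same sentence says that the two pairs are treated alike. Application of the second pair is fixed by sections 2.5.1 and 3.1 and by the timing in point 11.

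The most that can differ is one visible fit check per subject: two for Live against one for Clariti on the literal reading, two against two on the natural one. Visual acuity, both visible sets of scores and the 15-minute fit are repeated for both lenses on either reading. No effect on the primary or secondary scores is shown.

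The numbering mismatch itself is certain. That it is harmless rests on three assumptions: that site staff follow the stated intent of equal treatment, that the redacted parts of section 1.4 do not make the one-minute fit a named outcome, and that the redacted steps and Table 1 do not prescribe a deliberate difference between the pairs. An analyst who finds early fit recorded for only one lens would report the number of subjects behind each analysis, as section 3.4 already requires.
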